7.4.1.1 Definitions

Definition of adverse event (AE)

In a clinical study, an AE is any untoward medical occurrence (i.e. any unfavorable and unintended sign [including abnormal laboratory findings], symptom or disease) in a patient or clinical investigation subject after providing written informed consent for participation in the study. Therefore, an AE may or may not be temporally or causally associated with the use of a medicinal (investigational) product.

A surgical procedure that was planned prior to the start of the study by any physician treating the subject should not be recorded as AE (however, the condition for which the surgery is required may be an AE if worsens compared to baseline).

- Conditions that started before signing of informed consent and for which no symptoms or treatment are present until signing of informed consent are recorded as medical history (e.g. seasonal allergy without acute complaints).
- Conditions that started before signing of informed consent and for which symptoms or treatment are present after signing of informed consent, at *unchanged intensity*, are recorded as medical history (e.g. allergic pollinosis).
- Conditions that started or deteriorated after signing of informed consent will be documented as adverse events.

Definition of serious adverse event (SAE)

An SAE is classified as any untoward medical occurrence that, at any dose, meets any of the following criteria (a – f):

- a. Results in death.
- b. Is life-threatening.

The term 'life-threatening' in the definition refers to an event in which the patient was at risk of death at the time of the event, it does not refer to an event which hypothetically might have caused death if it were more severe.

- c. Requires inpatient hospitalization or prolongation of existing hospitalization.

A hospitalization or prolongation of hospitalization will not be regarded as an SAE if at least one of the following exceptions is met:

- The admission results in a hospital stay of less than 12 hours.
- The admission is pre-planned.
(i.e. elective or scheduled surgery arranged prior to the start of the study)
- The admission is not associated with an AE.
(e.g. social hospitalization for purposes of respite care).

However, it should be noted that invasive treatment during any hospitalization may fulfill the criterion of 'medically important' and as such may be reportable as an SAE

dependent on clinical judgment. In addition, where local regulatory authorities specifically require a more stringent definition, the local regulation takes precedence.

- d. Results in persistent or significant disability / incapacity.

Disability means a substantial disruption of a person's ability to conduct normal life's functions.

- e. Is a congenital anomaly / birth defect.
- f. Is another medically important serious event as judged by the investigator.

Serious adverse events

In addition to the SAE criteria specified in the standard text above, further criteria may be defined; e.g. all Grade-4 laboratory toxicities according to the Common Terminology Criteria for Adverse Events (CTCAE, version 4.03) may have to be recorded as SAEs.

7.4.1.2 Classifications for adverse event assessment

The descriptions and grading scales of Adverse events are found in the revised NCI Common Terminology Criteria for Adverse Events (CTCAE) version 4.03 which will be utilized for AE reporting. All appropriate treatment areas should have access to a copy of the CTCAE version 4.03.

- "Expectedness": AEs can be 'Unexpected' or 'Expected' for expedited reporting purposes only. 'Expected' AEs (the ASAEL) are bold and italicized in the CAEPR.
- Attribution of the AE:
 - Definite – The AE is clearly related to the study treatment.
 - Probable – The AE is likely related to the study treatment.
 - Possible – The AE may be related to the study treatment.
 - Unlikely – The AE is doubtfully related to the study treatment.
 - Unrelated – The AE is clearly NOT related to the study treatment.

All AEs will be assessed and documented by the investigator according to the categories detailed below.

All AEs will be assessed and documented by the investigator according to the categories detailed below.

7.4.1.2.1 Seriousness

For each AE, the seriousness must be determined according to the criteria given in Section 7.4.1.1.

7.4.1.2.2 Intensity

The intensity of the AE is classified according to the CTCAEv4.0. Grade refers to the severity (intensity) of the AE:

CTCAEv4 Grade 1: mild; asymptomatic or mild symptoms; clinical or diagnostic observations only; intervention is not indicated.

CTCAEv4 Grade 2: moderate; minimal, local, or noninvasive intervention is indicated; limiting to age-appropriate instrumental activities of daily living (ADL; instrumental ADL refers to preparing meals, shopping for groceries or clothes, using the telephone, managing money, etc.).

CTCAEv4 Grade 3: Severe or medically significant but not immediately life threatening; hospitalization or prolongation of hospitalization is indicated; disabling; limiting to self-

care ADL (self-care ADL refers to bathing, dressing and undressing, feeding self, using the toilet, taking medications, and not bedridden).

CTCAEv4 Grade 4: life-threatening consequences; urgent intervention is indicated.

CTCAEv4 Grade 5: death due to an AE.

7.4.1.2.3 Causal relationship

The assessment of the causal relationship between an AE and the administration of treatment is a clinical decision based on all available information.

The assessment is based on the question whether there was a "reasonable causal relationship" to the study treatment in question.

Possible answers are "yes" or "no".

An assessment of "no" would include:

1. The existence of a clear alternative explanation, e.g. mechanical bleeding at surgical site.
or
2. Non-plausibility, e.g. the subject is struck by an automobile when there is no indication that the drug caused disorientation that may have caused the event; cancer developing a few days after the first drug administration.

An assessment of "yes" indicates that there is a reasonable suspicion that the AE is associated with the use of the study treatment.

Factors to be considered in assessing the relationship of the AE to study treatment include:

- The temporal sequence from drug administration: The event should occur after the drug is given. The length of time from drug exposure to event should be evaluated in the clinical context of the event.
- Recovery on drug discontinuation (de-challenge), recurrence on drug re-introduction (re-challenge):
- Subject's response after de-challenge or subjects response after re-challenge should be considered in the view of the usual clinical course of the event in question.
- Underlying, concomitant, intercurrent diseases:
Each event should be evaluated in the context of the natural history and course of the disease being treated and any other disease the subject may have.
- Concomitant medication or treatment:
The other drugs the subject is taking or the treatment the subject receives should be examined to determine whether any of them may be suspected to cause the event in question.
- The pharmacology and pharmacokinetics of the study treatment:
The pharmacokinetic properties (absorption, distribution, metabolism and excretion) of the study treatment, coupled with the individual subject's pharmacodynamics should be considered.

[Causal relationship to protocol-required procedure(s)]

The assessment of a possible causal relationship between the AE and protocol-required procedure(s) is based on the question whether there was a "reasonable causal relationship" to protocol-required procedure(s).

Possible answers are "yes" or "no".

7.4.1.2.4 Action taken with study treatment

Any action on study treatment to resolve the AE is to be documented using the categories listed below.

- Drug withdrawn
- Drug interrupted
- Dose reduced
- Dose not changed
- Dose increased
- Not applicable
- Unknown

7.4.1.2.5 Other specific treatment(s) of adverse events

- None
- Remedial drug therapy

7.4.1.2.6 Outcome

The outcome of the AE is to be documented as follows:

- Recovered/resolved
- Recovering/resolving
- Recovered/resolved with sequelae
- Not recovered/not resolved
- Fatal
- Unknown

7.4.1.3 Assessments and documentation of adverse events

Safety laboratory samples will be analyzed at the *individual participating site laboratory*. Safety laboratory examinations will include hematology, biochemistry and urine examinations. Table 7.9.1.3:1 presents the laboratory tests to be performed.

Table 7.9.1.3:1 Clinical Laboratory Tests

Category	Parameters <keep parameters written in black; amend others as appropriate>
Hematology	hemoglobin, hematocrit, platelet count, blood cell count (WBC)

Table 7.9.1.3:1 Clinical Laboratory Tests

Category	Parameters <keep parameters written in black; amend others as appropriate>
Coagulation	International Normalized Ratio (INR), activated Partial Thromboplastin Time (aPTT),
Chemistry	
Electrolytes	sodium, potassium, calcium, magnesium,
Liver function tests	alkaline phosphatase, aspartate aminotransferase (AST), alanine aminotransferase (ALT), γ -glutamyltransferase (GGT), total bilirubin
Renal function parameters	Blood urea/blood urea nitrogen (BUN), creatinine; Creatinine clearance (see Section 13.6).
Other	glucose, albumin,

The investigator should complete additional evaluations of laboratory tests as clinically indicated. Any abnormal findings from these investigations need to be reported as an Adverse Event.

7.4.1.3.1 Assessment of other safety parameters

Physical examination, vital signs, height and weight

A full physical exam will include cardiopulmonary examination, examination of the regional lymph nodes, and examination of the abdomen and an assessment of the mental and neurological status. Additional symptoms which have not been reported during a previous examination will be clarified. Wherever possible the same investigator should perform this examination.

A complete physical examination will be done at Screening, Day 1, every visit on study, and at the End-of-Treatment visit. A symptom-directed examination is to be performed on all other visits.

Vital signs

Vital sign measurements blood pressure [systolic blood pressure, diastolic blood pressure], pulse rate, temperature and measurement of height (in cm, at screening) and body weight (in kg) and the evaluation of the ECOG performance status (see section 13.2) will be performed at the times specified in the flow chart.

7.4.1.4 Reporting of serious adverse events

Adverse event (AE) monitoring and reporting is a routine part of every clinical trial. Serious Adverse Events (SAEs) are reported by the participating site Lead Investigator within 24 hours to the Clinical Trial Network Monitoring Office (CTNMO) Manager ([name]) by email ([contact]) or by [contact]. The 24 hour paging number for the CTNMO Manager is [contact], [name]. The CTNMO Manager is then

responsible for reporting SAEs to the UAB IRB and protocol P.I. in accordance with study-specific requirements. SAEs occurring at CTNMO sites are reported to the UAB IRB as "non-UAB" events.

A Serious Adverse Event (SAE) is an AE that 1) results in patient hospitalization or prolongation of hospitalization; 2) results in persistent or significant disability or incapacity; 3) results in death; 4) is a cancer or congenital abnormality or 5) results in the development of drug dependence or abuse. An AE will be considered an SAE when the nature or severity of the event is not consistent with the current Investigator's Brochure. It is also the responsibility of the participating site Lead Investigator to report SAEs to the local site IRB and to submit copies of that report to the CTNMO Manager. It is the CTNMO Manager's responsibility to report the SAE to the Clinical Trials Monitoring Committee, UAB IRB and / or industry sponsor. This submission of IND Safety Reports will be cross referenced according to local regulations to Bayer Investigational Compound Number (IND) at the time of submission

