8.3 Statistical and analytical plans

The primary endpoint of the study is the rate of progression free survival (PFS) at 6 months (PFS6). Given the poor prognosis of this patient population and data from other studies of salvage therapy, a PFS6 of $\geq 20\%$ is felt to be important for this regimen, while a PFS6 $< 5\%$ is felt to be of poor interest. The trial also enrolls patients who progress within 6 months of last cycle of prior chemotherapy to enhance the interpretability of outcomes, since such patients are unlikely biologically to be progression-free for 6 more months without active therapy that favorably impacts on tumor biology to extend PFS. SAS version 9.3 was used to calculate power. The justification for the proposed sample size is based on an exact test for a binomial proportion with a one-sided significance level of 5%. With 32 evaluable subjects,

we will have approximately 80% power (79.6%) to reject the null hypothesis that PFS6 is < 5% in favor of PFS6 \geq 20%. Given that 5-10% of patients may be inevaluable, up to 35 patients may be enrolled. If five or more patients remain progression-free at 6 months, this regimen will be considered to be of significant interest.

Chi-square or Fisher's exact test will be employed to determine univariate association of biomarker status with PFS6 and objective response. Descriptive statistics including frequencies and proportions will be calculated to summarize safety and toxicity outcomes. Specifically, the number of adverse events (AE) and serious adverse events (SAE) will be tabulated and summarized. Point estimates and exact binomial (Clopper-Pearson) confidence intervals (CI) will be calculated to estimate the incidence of AEs and SAEs. The precision of these estimates, i.e., width of the confidence interval, will depend on the estimated incidence of each outcome. The table below gives the exact 95% confidence intervals for a range of incidences, assuming 32 evaluable subjects.

Number of subjects experiencing event	Estimated Incidence	95% Exact CI for Incidence		Width of CI
		Lower Limit	Upper Limit	
1	0.031	0.001	0.162	0.161
2	0.062	0.008	0.208	0.200
4	0.125	0.035	0.290	0.255
8	0.250	0.115	0.434	0.319
16	0.500	0.319	0.681	0.362

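### Section 7.4.1.4, which starts the 24-hour SAE clock, carries its own SAE definition that contradicts Section 7.4.1.1

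*Combined protocol and SAP*

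**What the plan says.** Section 7.4.1.1 opens its definition with "An SAE is classified as any untoward medical occurrence that, at any dose, meets any of the following criteria (a – f"). The six criteria are death, life-threatening ("Is life-threatening"), hospitalization or its prolongation, disability or incapacity, congenital anomaly, and a last category: "Is another medically important serious event as judged by the investigator". Three exceptions qualify the hospitalization criterion: a stay of under 12 hours, a pre-planned admission, and an admission not linked to an AE.

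Section 7.4.1.4 first sets the 24-hour report from the site to the coordinating office. It then gives a second definition, which begins "A Serious Adverse Event (SAE) is an AE that 1) results in patient hospitalization or prolongation of hospitalization", goes on to disability or incapacity and death, and ends with "4) is a cancer or congenital abnormality or 5) results in the development of drug dependence or abuse". The next sentence reads "An AE will be considered an SAE when the nature or severity of the event is not consistent with" the current Investigator's Brochure.

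Section 8.3 plans to tabulate AEs and SAEs. Point estimates with exact confidence intervals "will be calculated to estimate the incidence of AEs and SAEs".

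**The concern.** The text next to the 24-hour duty is the text a site is likely to use when deciding whether that duty applies. That text lacks two of the six criteria in 7.4.1.1 and adds a rule based on expectedness. Seriousness concerns the outcome or danger of an event; expectedness concerns whether the brochure already describes it. Merging the two can misclassify events in both directions.

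What is at stake is the timing of safety reports, the SAE label on individual events, and possibly the consistency of the SAE counts across sites. The PFS6 analysis, its decision rule and its power are not involved.

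**Working it through.** The plan states no SAE rate to reproduce, so the check compares the two definitions item by item.

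| Criterion | 7.4.1.1 | 7.4.1.4 |
|---|---|---|
| Death | yes | yes |
| Hospitalization or prolongation | yes, with three exceptions | yes, no exceptions |
| Disability or incapacity | yes | yes |
| Congenital anomaly | yes | yes |
| Life-threatening | yes | no |
| Medically important | yes | no |
| Cancer | no | yes |
| Drug dependence or abuse | no | yes |
| Not consistent with the brochure | no | yes |

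Four criteria are shared, two appear only in 7.4.1.1 and three only in 7.4.1.4. Neither list contains the other.

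Three kinds of event, classified literally under each section:

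1. A life-threatening event that the brochure describes at that severity, managed without admission and with no lasting disability. It is an SAE under 7.4.1.1 and not under 7.4.1.4.
2. A grade 1 event absent from the brochure, with no admission. It is not an SAE under 7.4.1.1 unless the investigator judges it medically important. It is an SAE under 7.4.1.4.
3. An AE-related admission of under 12 hours. The hospitalization criterion of 7.4.1.1 excludes it; 7.4.1.4 includes it.

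The brochure sentence also conflicts with Section 7.4.1.2, which reserves the expected/unexpected distinction for expedited reporting. The table in 7.4.1.4.2 points the same way: it requires no expedited report for grade 1 events, expected or not, while the brochure sentence would make the unexpected ones 24-hour SAEs. That table is damaged in the text available, so it is supporting evidence only.

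For scale in Section 8.3, one patient classified differently moves the estimated incidence by 1/32 = 3.1 percentage points with 32 patients, or 1/35 = 2.9 points with 35. This is the size of one step and does not estimate how many patients would be affected. The exact intervals printed in 8.3 for 32 subjects reproduce in every row; the interval method is not in question.

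**The case against.** The strongest reply is that the protocol already says which definition governs. Section 7.4.1.2.1 requires seriousness to be judged for each AE by the criteria in 7.4.1.1, and Section 7.4.1.4.1, itself part of 7.4.1.4, again points to 7.4.1.1. On that reading the second list is stray text. This has force, and a reader should not infer that the protocol has no governing definition. But 7.4.1.4 neither defers to 7.4.1.1 nor says which text prevails. It prints a complete alternative straight after the duty it controls.

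A reader might also infer that life-threatening events would go unreported. The documents do not support that. Section 7.4.1.4.1 requires all AEs to be reported up to 28 days after the last dose. Section 7.4.1.4.2 appears to require expedited reports for grade 4 and 5 events, with expected ones on a 10-calendar-day timeline as far as the damaged table can be read. Section 7.4.1.6 requires immediate notice of named events such as hepatic failure and gastrointestinal perforation, with no test of seriousness. What remains exposed is the 24-hour clock and the SAE label.

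A third inference would be that the SAE incidence in 8.3 will be biased. That is possible but not shown. Investigators record seriousness under a rule that names 7.4.1.1, and reporting also follows instructions in the Investigator Site File, which is not among the documents. Nothing shows that the tabulation would use the 7.4.1.4 list.

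**Conclusion.** The text is wrong as written: it is an internal contradiction in the safety-reporting rules. A site that follows 7.4.1.4 literally would leave a brochure-listed life-threatening event managed without admission out of the 24-hour SAE report, and would label a mild unlisted event as serious. The cross-references to 7.4.1.1 and the other reporting routes limit the practical effect mainly to the reporting clock and the label.

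The effect on the SAE counts in 8.3 depends on sites using different lists. The documents give no information on how often that would happen, so its size cannot be estimated. The conclusion rests on reading both sections literally and assumes that nothing in the Investigator Site File overrides 7.4.1.4. The point should be corrected but does not touch the primary analysis.

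**What to change.** In Section 7.4.1.4, replace only the numbered SAE list and the brochure sentence with a statement that SAEs are defined in Section 7.4.1.1. Keep the rest of the paragraph, because it holds the duties to report to the local IRB, the monitoring committee and the industry sponsor. Use expectedness only in Section 7.4.1.4.2, as 7.4.1.2 already intends.

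In the same edit, reconcile two statements on grade 4 laboratory toxicities. The end of the SAE definition in 7.4.1.1 says that further criteria may be defined and that these toxicities may have to be recorded as SAEs. Section 7.4.1.4.1 says that an isolated grade 4 laboratory abnormality is not reportable as an SAE unless it meets standard ICH criteria. Without this step, a pointer to 7.4.1.1 would still leave one category open.

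The cost is a two-sentence amendment plus the laboratory reconciliation, a reminder to sites, and a check of events already classified against 7.4.1.1. No new data collection is needed, and the analysis methods in 8.3 do not change.

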7.4.1.4.1 Routine Adverse Event Reporting

All Adverse Events **must** be reported in routine study data submissions. AEs reported must also be reported in routine study data submissions. Safety will be monitored throughout the study by physical examinations, review of adverse events (AEs), and laboratory studies. The frequency of safety monitoring procedures is outlined in Sections 6.6.1 and 6.9.1.3. Criteria that will be used throughout the study for dose interruption, reduction, and discontinuation of chemotherapeutic agents are specified in Section 6.3.1.1.

Data and Safety Monitoring Plan

The UAB Comprehensive Cancer Center Data and Safety Monitoring Plan (DSMP) will monitor subjects treated at UAB. The Clinical Trials Monitoring Committee (CTMC) on a weekly basis will closely monitor adverse reactions observed during treatment. The CTMC is responsible for data and safety monitoring of the trial and adherence to the DSMP. The independent Quality Assurance Committee (QAC) is responsible for oversight of the operation of CTMC, including adherence to the DSMP. Reports from the CTMC are reviewed monthly by the QAC.

Protocol Management and Oversight of Participating Site

[name] functions as the sponsor of the trial at UAB and at the participating sites. The participating sites will utilize their respective IRB of record. The Lead Investigator at participating site(s) will be responsible for ensuring that all the required data will be collected and entered onto the Case Report Forms. A monthly teleconference between UAB CTNMO and participating sites will ensure discussion of AEs seen across all sites. UAB PI, CTNMO manager and participating site Lead Investigators will discuss management of AEs and impact of AEs on trial conduct. The CTNMO office will report the outcome of these discussions at CTMC meeting every month. Periodically, monitoring visits will be conducted by CTNMO manager and the participating site Lead Investigator will provide access to his/her original records to permit verification of proper data entry. At the completion of the study, all case report forms will be reviewed by the CTNMO manager and will require his/her final signature to verify the accuracy of the data.

Table 7.9.1.4:1 AE/SAE reporting requirements

Time period	Reporting requirements
From signing of informed consent to ≤28	Report all AEs and SAEs regardless of relatedness or whether the trial drug was

days after last trial drug administration	administered. This includes all deaths.
Post-treatment (>28 days after last trial drug administration)	Report only SAEs which are considered related to trial treatment or trial design. Death should be reported as an SAE only when considered related to trial treatment or trial design (because death is an endpoint and will be followed-up separately).

The definition of serious adverse events (SAEs) is given in Section 7.4.1.1.

All adverse events, serious and non-serious, will be collected, documented and reported to the sponsor by the Lead site investigator on the appropriate CRFs / SAE reporting forms (Bayer SAE report form or alternatively the CIOMS form with Bayer cover letter form).

Reporting will be done according to the specific definitions and instructions detailed in the 'Adverse Event Reporting' section of the Investigator Site File.

For each adverse event, the investigator will provide the onset date, end date, CTC AE grade, treatment required, outcome, seriousness, and action taken with the investigational drug. The investigator will determine the relationship of the investigational drug to all AEs as defined in Section 6.9.1.1 and 6.9.1.2.

Adverse events with onset within first administration of Regorafenib therapy and 28 days after last administration of Regorafenib will be considered as on treatment. All AEs, including those persisting after end of study treatment will be followed up until they have resolved or have been sufficiently characterised or the principal investigator decides to not further pursue them.

Serious and non-serious adverse events occurring later than 28 days after last administration of trial drugs will only be reported in case they are considered drug-related or trial (procedure) related.

Each serious adverse event must be followed up until resolution or stabilization, by submission of updated reports to the designated person. An isolated laboratory abnormality that is assigned grade 4, according to CTCAE definition, is not reportable as an SAE; unless the investigator assesses that the event meets standard ICH criteria for an SAE. CTCAE grade 4 baseline laboratory abnormalities that are part of the disease profile should not be reported as an SAE, specifically when they are allowed or not excluded by the protocol inclusion/exclusion criteria.

All serious adverse events will be reported to UAB IRB.

All serious adverse events should be reported to Bayer within 24 hours. In the event of such an event, the investigator should refer to the Pharmacovigilance section of the contract for reporting procedures.

